Important Secondary Endpoints:

- (1) Reduction in mean number of SUI episodes per day from the 7-day baseline period to the last 7 days of the 14-day device treatment period. Participants will record SUI episodes in the Study Diary during the baseline (7 days) and treatment (14 days) periods. Negative values are indicative of efficacious outcome.
- (2) Change in Quality of Life as Measured by the ICIQ-LUTSqol Quality of Life Questionnaire.

The Quality of Life Questionnaire to be performed at baseline, before, and after treatment phase of the study is based on 20 questions referring to areas which may have been influenced or changed by accidental urine loss and/or prolapse. These questions are assigned a value of, 1 = 'Not at all,' 2= 'Slightly,' 3 = 'Moderately,' or 4 'A lot.' Each area is then assessed on a scale of 1-10 to see how much it bothers them. The Questionnaire is scored by taking the average score of items and then multiplying that value by 25 to put scores on a scale from 0 to 100. A lower score is considered less impact to quality of life and a higher score reflects more impact to quality of life. In the same manner, a reduction in scores from baseline reflects improved quality of life. A reduction in

score of ≥ 3.7 is considered the Minimum Clinically Important Difference (MCID).

- (3) Evaluation of Adverse Event assessments to determine device is safe for use.

Important Exploratory Endpoints:

- (1) Participants can successfully use the device in accordance with the given Instructions for Use.
- (2) Participants will find the device comfortable enough to demonstrate compliance with the study procedures during the device treatment phase.

Population: Approximately 50 female participants over the age of 18 who have been physician diagnosed with Stress Urinary Incontinence; have a normal voiding history; are familiar with the use of tampons; and have had a Normal Pap Smear <36 months prior to study enrollment.

Phase: Efficacy and Safety

Number of Sites enrolling participants: 4

Description of Study Agent: A disposable stress urinary incontinence pessary device worn daily for 12 hours.

Endpoint Classification:	Efficacy and Safety Study
Interventional Model:	Single Group, Open Study
Masking:	Open Label
Primary Purpose:	Efficacy and Safety

Study Duration: 6-12 months

Participant Duration: 2 months

SCHEMATIC OF STUDY DESIGN

Prior to Enrollment (Screening)

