Total N: Obtain informed consent. Screen potential participants by inclusion and exclusion criteria; obtain and document medical history. Confirm that participant symptoms indicate SUI diagnosis. Perform the urine pregnancy test (if applicable), urinalysis, vaginal examination and symptom evaluation to ensure participant has no active urinary or vaginal infection requiring treatment. A vaginal swab will be performed to establish baseline vaginal microflora. Perform usability and fit assessment test.

NOTE: Results of the SUI diagnosis assessment and fit assessment may deem participant ineligible for enrollment due to urge incontinence or mixed (stress and urge) incontinence diagnosis or poor /improper fit. To simulate OTC use, participants will be asked to perform self-selection and assess fit based on the product labeling prior to confirmation by the PI.

Enrollment/Visit 1 Time Point

Total N: Complete a questionnaire by the physician. Participant will also complete a baseline Quality of Life Questionnaire.

Participant will receive 14 preweighed pads to take home. Participant will perform control phase of study wearing pads for 12 hours/day for 7 consecutive days. Pads will be returned by participant for weighing and data collection.

NOTE: Results of the laboratory tests from the screening visit (pregnancy test, vaginal examination and urinalysis test) may deem a participant ineligible for enrollment due to positive pregnancy result, positive vaginal infection requiring treatment, or positive urinary infection requiring treatment, respectively.

Visit 2 Time Point

Total N: Urine pregnancy test, if applicable, to rule out pregnancy, vaginal examination, and symptom evaluation will be repeated to rule out any potential infection requiring treatment. Vaginal swab will also be repeated to evaluate changes in vaginal microflora. Quality of Life questionnaire will be repeated. Participants will be given 20 study devices and 28 preweighed pads to perform the treatment phase of the study. Participants will wear 14 devices and 14 pads simultaneously for 14 consecutive days. Pads will be returned by participant for weighing and data collection, and participants will record information regarding activity level and quality of life.

Visit 3 Time Point

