A study comparing cost utility of different treatment options revealed that incontinence pessaries were the most cost effective. Pessaries have been found to increase continence by 64-75%. While 50-75% of women decline pessaries when recommended, over three quarters of patients that use the pessary continue to use after one year. Studies have also revealed that women do not perceive any difference in the effectiveness of pessary treatment versus physical therapy treatment; however, pessary use is also associated with pain, irritation, UTIs and difficulty in physician fitting of the pessary.

A study performed to evaluate the efficacy and safety of a novel disposable intravaginal device for the treatment of SUI was performed at 2 sites in Israel. Sixty women were recruited and enrolled into the study and used the device for 28 – days after a 7-day control period. During the control period, preweighed pads were worn daily for 8 hours to determine a baseline for participants. This period was followed by a 28-day usage period. The last 14 days of the control period were used to allow for participants to find the right size device. The primary endpoint was

the percentage of women who achieved a $\geq 70\%$ reduction in pad weight gain (PWG) from the control period to the last 14 days of device usage. The results demonstrated that 85% of participants met the success criteria. The device was concluded to be easy to use, well-tolerated, and effective in reducing SUI³.

As is recommended in the Guidance for Industry and FDA Staff: Clinical Investigations of Devices Indicated for the Treatment of Urinary Incontinence, the Rinovum Subsidiary 2, LLC. SUI Device Pivotal Study will include the use of a voiding diary to document leakage occurrence daily. Also, as recommended in the guidance, the study will use pad-weighing to monitor efficacy of the device. The 24-hour test parameter will be used, but will be tailored to be in line with the amount of time the device will be used for treatment each day (12 hours). Participants will be provided with ziplock bags and mailers so that used pads can be collected daily and weighed by the site clinical team within 48 hours to determine the amount of pad weight gain (PWG). Note that more than 1 pad may be worn throughout each day depending on the amount of leakage protection required.

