5.4 PARTICIPANT WITHDRAWAL OR TERMINATION

Participants are free to withdraw from participation in the study at any time upon request. An investigator may terminate participation in the study if:

- Any clinical adverse event (AE), laboratory abnormality, or other medical condition or situation occurs such that continued participation in the study would not be in the best interest of the participant
- The participant meets an exclusion criterion (either newly developed or not previously recognized) that precludes further study participation.]

Data for patients lost to follow up/withdrawal will be collected if possible. Subjects in the ITT population but not in the mITT group will be represented in all tables except those for the primary and secondary endpoint analysis. Data from those withdrawing from or lost to follow-up in the mITT population will be used for the primary endpoint and, if there is at least one full day's worth of data on the number of SUI episodes available, then this subject will also be included in the analysis of change in number of SUI episodes. Attempts will be made to contact subjects withdrawing from or lost to follow-up to the mITT population to administer the QoL questionnaire. If successful these subjects will be included in the change in QoL analysis. For mITT subjects not completing the treatment phase, a "last observation carried forward" approach will be used (see section 10 "Statistical Considerations"). If it appears that there will not be 50 subjects in the PP population further recruitment and enrollment will be necessary.

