10 STATISTICAL CONSIDERATIONS

10.1 Populations

Intent to Treat Population (ITT): Any subject enrolled who gets a pre-weighed pad for the control phase. This is expected to be 60-70 subjects.

Modified Intent to Treat Population (mITT): Any subject enrolled who gets through the control phase, is given the device and pads for the treatment period, and who uses the device such that there is at least one data point to analyze - i.e., use of the pad for at least one hour during the last 7 days of the treatment period. A subject who is not in the study at the beginning of the last 7 days of the treatment period is in the ITT population but not the mITT population. **THE mITT IS THE POPULATION THE ANALYSIS WILL BE DONE ON.**

Per Protocol Population (PP): Any subject getting through the entire treatment period and has complete data (i.e., pad weight reduction data for the last 7 days of the treatment period). For example, someone having only data for 6 out of the last 7 days of the treatment period is in the mITT population but not the PP population.

Safety Population (SP): Same as ITT.

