Power and sample size calculations determine scenarios of success. When the resulting mean reduction in pad weight gain per hour is quantified, its lower limit of a $(1-0.0167)\%$ confidence level is determined. This value is then compared to parameters determined to be efficacious in the sample size calculations (section 10.3). It is expected that the mean reduction per hour will be >50% such that the lower limit of the confidence interval for that result will be higher than 50% with adequate power to suggest success for the study.

3. Secondary Endpoints:

- a. For the change in SUI episodes endpoint each subject will have a change in the number of episodes per day from the control period to the treatment period. Specifically, the number of episodes will be recorded each day in the diary. For the control phase, there will be (at most) 7 days of data. The mean number of SUI episodes per day will be computed for each subject. The same measures

will occur in the treatment period for the analysis period, the last 7 days. Each subject will again have a mean number of SUI episodes per day. If the pads are not worn for the entire time specified during a day, the fraction of the day the pads are worn will be used in computing the number of days. Therefore, there will be, say, 50 differences comprised of mean number of SUI episodes per day in the treatment period minus mean number of SUI episodes per day for control period. (These numbers will likely be negative.) The mean of these 50 mean differences represents the mean change in the number of SUI episodes per day from the control period to the treatment period. The null hypothesis will then be that the mean change in the number of SUI episodes is 0, and the alternative is that it is less than 0, analyzed using a paired t-test. A p-value of less than 0.0167 indicates success.

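### The SUI-episode rate divides a daily diary count by pad-wear time without tying both to the same hours, so unequal pad wear between periods can bias the change.

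*Combined protocol and SAP*

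**What the plan says.** **Numerator.** Section 10.4(3a) says that "the number of episodes will be recorded each day in the diary", and a mean per day is formed for each woman in each period. The Protocol Summary gives the diary instruction without hours: "Participants will record SUI episodes in the Study Diary during the baseline (7 days) and treatment (14 days) periods". Section 7.3 describes the baseline diary as a record of leakage over that phase. Section 5.4 admits a withdrawn mITT subject to the episode analysis if there is "at least one full day's worth of data on the number of SUI episodes available".

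**Denominator.** Section 10.4(3a) adds that, when pads are not on for all of the specified time, "the fraction of the day the pads are worn will be used in computing the number of days". The specified time comes from the Schematic of Study Design: "wearing pads for 12 hours/day for 7 consecutive days". Section 2.1 also mentions 12 hours, but there it explains how the 24-hour pad test was shortened. It does not describe the diary.

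**Test.** The change is treatment minus control, using the last 7 treatment days. The null is a mean change of zero; "the alternative is that it is less than 0, analyzed using a paired t-test", one-sided at 0.0167 in the mITT population. Section 10.1 lets a woman into that population with "use of the pad for at least one hour during the last 7 days of the treatment period". Section 10.4(1) makes this one of three endpoints meant to support labeling.

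**The concern.** Pad-hours are the right exposure for what a pad absorbs, which is why the primary endpoint is expressed per hour of wear. An episode that a woman notices and writes down can happen with or without a pad. If the diary collects episodes over the whole day while the denominator shrinks with pad time, a short-wear day gives a higher rate with no change in leakage.

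The test compares two periods against a null of zero, so any systematic difference in wear between them passes straight into the estimate. The periods are not alike: pads alone in the first, pads plus device in the second, with comfort and compliance listed as open questions in Section 4.3. The trial has one arm, so no concurrent control would reveal the artifact. A labeling claim could be gained or lost through wear time alone.

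**Working it through.** **The plan's own figure.** The only number attached to this endpoint is its alpha: 0.05/3 = 0.0167, which reproduces. Table 1 in Section 10.3 concerns the primary endpoint. No standard deviation, effect size or expected wear is given for episodes.

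**Assumptions, not from the documents:** 1 to 3 episodes per day; wear of 9 to 12 hours; device worn for the same hours as the pads; fraction taken as hours/12.

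**Formula.** Rate = episodes per day ÷ (pad-hours/12). Change = treatment rate − control rate.

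**Whole-day diary, 2 episodes per day in both periods, no device effect**

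| Pad-hours, control / treatment | Control rate | Treatment rate | Change |
|---|---|---|---|
| 12 / 12 | 2.00 | 2.00 | 0 |
| 9 / 12 | 2/(9/12) = 2.67 | 2.00 | −0.67 (false drop of 25%) |
| 12 / 9 | 2.00 | 2.67 | +0.67 (false rise of 33%) |
| 9 / 9 | 2.67 | 2.67 | 0 |

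**Diary confined to pad-wear hours, true rate 2 per 12 hours.** Nine hours yields 2 × 9/12 = 1.5 episodes, and 1.5/(9/12) = 2.00. The rule is then a correct exposure adjustment and the change is 0 whatever the wear.

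**Effect on the test.** Simulation of 4,000 trials of 50 women, 7 days per period, Poisson counts with gamma variation between women (shape 2), one-sided paired t-test at 0.0167:

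| Whole-day diary; control / treatment hours | Mean 1 per day | Mean 2 | Mean 3 |
|---|---|---|---|
| False-positive rate, 11 / 12 | 0.15 | 0.27 | 0.41 |
| False-positive rate, 10 / 12 | 0.56 | 0.87 | 0.97 |
| Power, 25% reduction while device is worn, 12 / 12 | 0.89 | 0.995 | 1.00 |
| Power, same effect, 12 / 10 | 0.06 | 0.11 | 0.15 |

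In the last row a little of the loss is genuine, because the device is in for less time. At a mean of 2, the count falls to 2 × (1 − 0.25 × 10/12) = 1.58, a true change of −0.42. The rule turns this into 1.58/(10/12) = 1.90, a change of only −0.10. With entries confined to wear time, the simulated false-positive rate was 0.014 to 0.021 across all wear patterns.

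**Base of the fraction.** The adjustment applies only when wear falls short of the specified time, so full wear counts as one day, which suggests a 12-hour base. Read literally, a fraction of the day could mean 24 hours: 9 hours would then be 9/24 = 0.375 of a day and the rate 2/0.375 = 5.33 instead of 2.67.

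**Extreme values.** On the whole-day reading, a woman with one diary day, 2 episodes and 1 pad-hour scores 2/(1/12) = 24 per day. In a sample of 50 this moves the mean by (24 − 2)/50 = 0.44. A day with diary entries but no pad adds nothing to the denominator, and the text does not say whether its episodes count.

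**The case against.** The strongest reply is that the whole-day diary is inferred. Section 10.4(3a) treats full specified wear as one day, which makes good sense if its authors had in mind episodes during wear, in parallel with the per-hour scaling of pad weight. The diary forms are not among the documents and may define the window or capture times. Section 10.2 leaves further analysis detail to a separate SAP. This stands, and it means the bias cannot be asserted as fact. It does not remove the gap: the protocol never links the diary window to wear time, and the full-day condition in Section 5.4 leans towards whole-day counting without settling it.

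A reader might also infer that short wear by itself distorts the result. It does not: equal short wear leaves a null change at zero. Nor do the documents say which way wear would differ. Discomfort in the treatment phase, the most obvious cause of short wear, would work against the device.

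Finally, a reader might conclude that the fraction rule should simply be deleted. If entries are confined to wear time, that would introduce bias. At a constant 2 episodes per 12 wear-hours, 12 hours in control and 9 in treatment would give 2.0 against 1.5, a false drop of 25%.

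**Conclusion.** The concern holds conditionally. The plan leaves undefined both the diary's counting window and the base of the fraction, and it does not tie the window to the pad-hours in the denominator. If the diary covers the whole day, unequal wear between the control week and the last 7 treatment days biases the change in either direction. One hour's systematic difference is enough to matter: at an assumed 2 episodes per day, control wear of 11 hours against 12 in treatment raises the simulated false-positive rate from the nominal 0.0167 to 0.27. If entries are confined to wear time, there is no bias.

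The episode rates and wear hours used here are assumptions, so the sizes illustrate sensitivity and do not predict this trial's error. The documents do not support a claim that the endpoint is certainly biased. They do support requiring that numerator and denominator be matched before data are analysed, because the rule as written gives a wrong result on the plain reading of the diary instructions.

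**What to change.** Make the episode count and its denominator cover the same hours in both periods, and say so in Section 10.4(3a) and in both diaries.

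- **Preferred.** Have the diary mark each episode as pad-on or pad-off, or record its time. Count only pad-on episodes and divide by pad-hours/12, with the 12-hour base stated.
- **Alternative.** State that the diary covers the whole day, divide by completed diary days and remove the pad-fraction sentence. Use this only if the diary really is whole-day.

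Under either option, state how days with diary entries but no pad wear are handled. The cost is one diary column and slightly more recording for participants under the first option, or a rewritten sentence under the second. Pad-wear hours are already needed for the primary endpoint.

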10.4 Statistical Hypotheses and Data Description

1. Type 1 Error and Multiplicity Concerns:

The inferential tests for the one primary and two secondary endpoints were initially conceived to be one-sided using alpha=0.05. Since the sponsor wishes to use the success of all three for labeling and marketing purposes, a Bonferroni adjustment for multiple comparisons will be employed. Thus, statistical significance will be indicated for each endpoint if the p-value is less than 0.0167.

2. Primary Endpoint:

There is one primary endpoint, for efficacy. The objective is to show that reduction in the mean pad weight gain per hour is >50% in the treatment period. Thus, the null hypothesis is that the mean weight gain reduction per hour is <=50%, and the alternative is that it is >50%, from the control period (no device) to the treatment period (women wearing the device). The data values will be computed for each woman as:

[(total weight of all pads worn during the treatment period/hrs. pads are worn during treatment)

minus

(total weight of all pads worn during the control period/ hrs. pads are worn during control)]

The above quantity divided by
(total weight of all pads worn during the control period/ hrs. pads are worn during control)

This resulting quantity is then multiplied by 100.

Ex. Subject's total pad weight for control period is 140 grams. Pads were worn for a total of 100 hours. Weight/hr. is $140/100 = 1.4$ g/hr. Subject's total pad weight for treatment period is 60 grams. Subject wore pads for 100 hours. Pad weight per hour is $60/100 = 0.6$ g/hr. Difference, treatment – control is $0.6 - 1.4 = -0.8$ g/hr. For the percent change, $100 * (-0.8/1.4) = -57.143\%$. Therefore the reduction in pad weight gain is 57.143%.

The null hypothesis will be that the mean reduction in pad weight gain per hour is less than or equal to 50%, with the alternative that it is greater than 50%. If the raw percentage change data appear to be normally distributed, a paired t-test will be used to test the hypothesis. If not, see section 10.6 (2).

The precision method will be utilized to determine success. The precision approach creates a lower bound for a confidence interval that is higher than the reference, in this case 50%. This 50% standard was chosen based on the FDA guidance document.

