- b. For the quality of life score there will be three measures as described in the visit schedule above. For descriptive purposes the results and change from the previous visit will be shown, as well as the change from the enrollment visit to the post-treatment visit. The changes will likely be negative scores as the QOL is expected to improve, as the instrument records lower numbers as indicating a better quality of life. For the purposes of inferential analysis, a mixed model analysis of variance on the scores will be used on the result at time t (t=baseline, post-control, post-treatment) with time as a fixed effect and subject as a random effect. Thus, the null hypothesis is that there is no significant difference from baseline/enrollment to post-treatment, i.e., that the mean change in score is 0. The alternative is that this change is less than 0. Correlation of scores within subjects will be considered as compound symmetric. The p-value indicating the significance of the least square mean score at the third time-point compared to that at the first time-point will determine if the endpoint is met.

All inferential testing will be done on the mITT population and will be one-sided. As noted above statistical significance will be reached if the relevant p-value is less than 0.0167. Results for all populations will be reported.

There is a secondary safety endpoint as described earlier in the protocol. Safety reporting using urinalysis, vaginal swab, vaginal examination, and evaluation will be descriptive and narrative in nature.

Similarly, exploratory endpoint results of comfort and successful use will be descriptive. No inferential hypotheses will be used here.

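### The QoL model fixes compound symmetry over two pre-device scores and one post-device score, so the standard error of the deciding contrast can be too small and its type I error above 0.0167

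*Combined protocol and SAP*

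**What the plan says.** Section 10.4 (1) explains that the tests "were initially conceived to be one-sided using alpha=0.05". It then divides alpha by three because the sponsor wants all three endpoints for labeling and marketing: "statistical significance will be indicated for each endpoint if the p-value is less than 0.0167". Section 10.4 (3) adds: "All inferential testing will be done on the mITT population and will be one-sided".

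Item 3b specifies the QoL model, with scores at three times ("t=baseline, post-control, post-treatment) with time as a fixed effect and subject as a random effect"). On covariance it says: "Correlation of scores within subjects will be considered as compound symmetric". One contrast decides the endpoint: "significance of the least square mean score at the third time-point compared to that at the first time-point will determine if the endpoint is met".

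The Schematic of Study Design gives the timing. At Visit 1: "Participant will also complete a baseline Quality of Life Questionnaire". At Visit 2, after the pads-only week: "Quality of Life questionnaire will be repeated. Participants will be given 20 study devices and 28 preweighed pads to perform the treatment phase". The third score is taken at Visit 3, after the treatment phase. Scores one and two therefore both precede treatment-phase use of the device.

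The plan names no other covariance structure, no check of this one, no robust standard error and no paired sensitivity analysis. The only fallback for QoL is a log transformation (10.6). Section 10.7 may add site as a fixed effect. Neither changes the assumed correlation.

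**The concern.** Compound symmetry assumes one variance and one correlation for every pair of visits, so it treats the three pairwise differences as equally variable. The visit schedule gives reason to doubt that. The first two scores are separated nominally by one week without the device. The first and third are separated by the longest interval in the study and by the intervention. If the third-minus-first difference is the most variable of the three, the model averages it with quieter differences and reports too small a standard error for the contrast that decides success.

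At stake is the error rate of a secondary endpoint intended for labeling, for which the plan deliberately tightened alpha to 0.0167.

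**Working it through.** **Inputs from the documents.** One-sided alpha 0.05 split over three endpoints; three QoL scores; deciding contrast time 3 minus time 1; sample size 50 (section 10.3).

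**Assumed.** All QoL correlations and SD ratios, since the documents give none; complete data; normal scores.

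**Step 1: the plan's own figure.** 0.05 / 3 = 0.01667, which rounds to the stated 0.0167.

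**Step 2: the model's standard error.** Let V12, V13 and V23 be the true variances of the pairwise differences. With complete data, the compound-symmetric model is repeated-measures ANOVA:

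- Model SE of (time 3 − time 1) = √(2·MSE/n) on 2(n − 1) = 98 df, where the expectation of 2·MSE is (V12 + V13 + V23)/3.
- True SE = √(V13/n).
- Ratio of model SE to true SE ≈ √[(V12 + V13 + V23)/(3·V13)].

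The ratio is below 1 exactly when V13 exceeds the average of the three.

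**Step 3: numbers in.** With equal SDs of 1, Vjk = 2(1 − rjk). Two examples:

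- r12 = 0.8, r13 = r23 = 0.6: V = 0.4, 0.8, 0.8; average 0.667; ratio √(0.667/0.8) = 0.913.
- r12 = 0.9, r13 = r23 = 0.5: V = 0.2, 1.0, 1.0; average 0.733; ratio √(0.733/1.0) = 0.856.

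**Step 4: type I error.** Simulated at n = 50 against a nominal one-sided 0.0167, with 100,000 to 400,000 trials per pattern; repeat runs differ by about 0.001.

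| Assumed pattern (r12 / r13 = r23 unless stated) | Model SE / true SE | Type I error |
|---|---|---|
| Compound symmetry true, all 0.7 | 1.00 | 0.017 |
| 0.7 / 0.6 | 0.96 | 0.020 |
| 0.8 / 0.7 | 0.94 | 0.022 |
| 0.7 / 0.5 | 0.93 | 0.024 |
| 0.8 / 0.6 | 0.91 | 0.026 |
| 0.8 / 0.5 | 0.89 | 0.028 |
| 0.9 / 0.5 | 0.86 | 0.034 |
| AR(1), 0.8 per visit | 0.84 | 0.037 |
| Exponential decay, 0.9 per week, weeks 0, 1, 3 | 0.83 | 0.039 |
| Reverse: 0.5 / 0.7 | 1.11 | 0.010 |

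Using the contrast's own variance (a paired t-test, equivalent to an unstructured matrix with complete data) gives 0.016 to 0.017 in every row. A larger sample does not help: 0.9 / 0.5 at n = 65 still gives 0.034.

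**Step 5: price of dropping the restriction.** If compound symmetry were true, the critical t would go from 2.158 (98 df) to 2.189 (49 df): 2.189/2.158 = 1.014.

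**Step 6: effect on the family.** The other two tests stay at 0.0167 each, so the Bonferroni bound becomes 0.0334 plus the QoL error: 0.053 to 0.062 for QoL errors of 0.020 to 0.029, and 0.067 to 0.072 for 0.034 to 0.039, against the intended 0.05.

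**The case against.** **No size can be read from the documents.** They contain no QoL SD or correlation. A reader might infer that the QoL type I error is doubled; that is not supported. Doubling is the top of the plausible range: with equal SDs and r13 = r23 it needs something like 0.9 / 0.5. This part of the objection stands.

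**Under the null, device status alone explains little.** If the device changes no woman's QoL, it cannot lower the pre-post correlation. Only elapsed time can, or device effects that differ between women yet average zero. Pure time decay does reach 0.036 to 0.039, but it assumes no stable trait and no measurement noise. With an assumed stable trait, decay and noise together, the error is 0.019 to 0.024. This also stands, and makes the milder figures at least as credible as the larger ones.

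**The one-week gap is nominal.** The schedule table gives no window for Visit 2. Women may time treatment around menses or travel (2.2), and a vaginal infection may delay it (7.3). A longer gap weakens the case for a very high correlation between the first two scores. It does not remove the asymmetry, because time 1 to time 3 is still the longest interval.

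**The test could be conservative.** A reader might infer that success will be declared too easily. If V13 is below the average, the opposite happens.

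**Other outputs and a later SAP may help.** Item 3b also reports the enrollment-to-post-treatment change, and 10.2 calls for means and SDs, so a paired test could be reconstructed. Section 10.2 also promises a more detailed SAP. But 10.4 already fixes the structure, and descriptive tables do not alter the decision rule.

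**Conclusion.** The point holds as a conditional one. The plan imposes a covariance restriction that the design gives reason to doubt, on the one contrast that decides the QoL endpoint, with no check or alternative. The direction follows by algebra once V13 exceeds the average pairwise variance, and the schedule makes that the likelier case.

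The size rests on assumed correlations, n = 50 and complete data; missing Visit 3 scores were not simulated. The defensible range runs from about 0.010 (reverse pattern), through nominal, to 0.020 to 0.029 for mild to moderate departures and 0.034 to 0.039 for strong ones.

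The effect is confined to QoL. A reader might infer that the study-wide error doubles, but the primary and SUI-episode tests are unaffected and the family bound rises to at most about 0.072 in these scenarios. If the QoL benefit is large, the conclusion may not change. It is worth correcting because the risk is avoidable, the endpoint is meant for labeling, and the correction is nearly free.

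**What to change.** In section 10.4 (3b), replace compound symmetry with an unstructured covariance matrix for the three visits (six parameters, readily estimated with about 50 women), with Kenward-Roger degrees of freedom, and keep the time 3 versus time 1 contrast. Because the unstructured matrix already carries the within-subject correlation, the separate random subject effect should be dropped. Carry the same structure into the log-scale and site-adjusted versions.

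A paired t-test of the third-minus-first change would also serve. It matches the analysis already planned for SUI episodes and has nominal error with complete data.

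The cost is a sentence in the plan and a small change to the SAS code. If compound symmetry were in fact true, the critical t would be about 1.4% larger (2.158 to 2.189).
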